PART B STUDY DESCRIPTION

| TITLE OF PROTOCOL | Effectiveness of Ablative Fractional 2940 nm Laser Treatment for Vulvar Lichen Sclerosus |
|------------------------|--|
| Principal Investigator | [name] |

B1. PURPOSE OF PROTOCOL

The object of this non-randomized, prospective study is to assess the effectiveness of ablative fractional 2940 nm laser treatment of vulvar lichen sclerosus.

Aim 1: To assess physical and histological changes related to vulvar lichen sclerosus before and after laser treatment.

Aim 2: To evaluate participant satisfaction for laser treatment of vulvar lichen sclerosus.

The results of this study will determine whether fractional 2940 nm laser is an effective treatment option for lichen sclerosus, particularly for those participants not eligible for high-dose topical steroids or who have failed prior treatment with topical steroids.

B2. SIGNIFICANCE AND BACKGROUND FOR THE STUDY

Vulvar lichen sclerosus is an autoimmune condition affecting the epithelial lining and dermis of the anogenital region. On gross visual exam, vulvar lichen sclerosus is often described as ivory-white plagues or patches extending from the clitoris to the labia majora, perineum, and perianal region.⁷ This inflammatory dermatologic condition causes thinning of overlying tissue, resulting in pruritus, pain, dyspareunia, and dysuria. Affected tissue is often compromised by symptoms of pruritus that cause scratching, leading to trauma to the skin such as excoriations, ecchymoses, fissures, and edema. The chronic inflammatory state often induces loss of vulvar architecture, including instances of flattening of the labia majora and minora, fusion between the prepuce and clitoris, and narrowing of the vaginal introitus. These physical changes to the anogenital regional further exacerbate symptoms. Additionally, physical symptoms are compounded by dyspareunia and inability to comfortably have intercourse, which can influence sexual behavior and mental well-being. This chronic condition can often result in feelings of "isolation, hopelessness, depression, anxiety, anger, and low-self-esteem." Vulvar lichen sclerosus most commonly affects prepubertal and perimenopausal or postmenopausal women, with an incidence of 14.6 per 100,000 women.² The etiology remains unknown, with many possible multi-factorial components such as hormones, genetics, presence of other autoimmune conditions, and local and environmental factors acting as potential causes.

Vulvar lichen sclerosus is often diagnosed by gross physical exam and participant report of symptoms, but is definitively diagnosed by biopsy of affected tissue. Histologically, vulvar lichen sclerosus commonly exemplifies hyperkeratosis, epidermal atrophy, basal cell degeneration, dermal hyalinization, and lymphocyte infiltration.⁵ Women with untreated or poorly controlled lichen sclerosus are at a higher risk for squamous cell carcinoma of the vulva, further supporting the need for definitive treatment, even in asymptomatic participants.⁴ First-line treatment has traditionally involved super potent topical corticosteroids, such as clobetasol or halobetasol. Treatment generally involves daily application initially for 2-4 weeks and then 2-3 times weekly for maintenance. Side effects from these topicals include skin atrophy, telangiectasia, and striae.⁷ Super potent steroids have been compared to other topical agents such as testosterone and progestin, and found to be superior and result in statistically significant improvement in comparison.⁵ However, not all patients are eligible for treatment with high-dose topical steroids.

Although super potent steroids are the mainstay of therapy, they are not without risk or adverse effects. Such steroids can cause atrophy, telangiectasia, and striae, particularly in non-hair bearing areas. In those participants with particularly resistant disease or skin changes not penetrable by topical steroids, intralesional corticosteroids, topical calcineurin inhibitors, or retinoids are other potential alternatives.

One proposed alternative treatment involves laser therapy with CO₂. In 1982, Rosemberg and Jacobs first brought to light the use of CO₂ laser as a successful treatment of penile lichen sclerosus.⁹ Since that time there have been numerous small case studies regarding CO₂ laser treatment and its application to vulvar lichen sclerosus and other dermatological conditions, such as vulvovaginal atrophy and genitourinary syndrome.^{1,3,6,8,9,10} Laser therapy functions by using heat to ablate the epidermis and dermis.³ As a result, hyperkeratotic skin is ablated with microthermal injury inducing a rapid process of repair,⁶ revealing new normal functioning epidermal-dermal junction without previously dysregulated signaling.³

In a study involving 21 perimenopausal women with vulvovaginal atrophy, Arroyo et al. treated women with fractional CO₂ laser over a series of 3 treatments and then reevaluated symptoms and tissue 12 and 24 weeks later via vaginal health index (VHI) scores.¹ At 12 weeks, 82% of patients had significant improvement in VHI. Additionally, 97% of patients reported no to mild discomfort with treatment. Itching was the most commonly reported side effect (20%).

Lee et al. used ablative CO₂ laser and fractional CO₂ laser therapy on five patients with hyperkeratotic vulvar lichen sclerosus that was previously unresponsive to topical steroids. This study included five women with vulvar lichen sclerosus recalcitrant to topical treatment with clobetasol propionate 0.5% ointment as evidence by ongoing symptoms and gross physical exam. Of the 4 women who reported symptoms before treatment, 100% experienced improvement after CO₂ laser treatment. Coyle also used laser therapy via the ProFractional Er:YAG Fractional Ablative Laser (Sciton, Inc.). This study is unique in that pretreatment biopsies were used to determine depth of vulvar lichen sclerosus. Using this histologically determined depth, the investigator individualized depth of laser treatment to match over 3 laser treatment sessions. A total of 15 patients were enrolled, and at 3 months, a repeat biopsy showed 7 participants (58.3%) had no vulvar lichen sclerosus with 41.6% of participants reporting improvement in symptoms compared to baseline. Peterson et al. also had successful results in two patients using CO₂ laser therapy with a treatment protocol that involved two passes of the CO₂ laser or until there was no evidence of disease present.⁸

Another consideration related to laser therapy is long-term results. Windahl et al. evaluated 62 male patients who had histologically proven lichen sclerosus and treated with CO₂ laser therapy. Of the 62 men evaluated, 50 were available to interview and 80% reported no recurrence of symptoms; median follow-up was 14 years.

The laser to be used in this study is the ProFractional Er: YAG 2940nm laser from Sciton, Inc. This device has been approved by the FDA for use in ":surgical applications requiring the excision, incision, ablation, vaporization, and coagulation of soft tissue, and for skin resurfacing. Soft tissue includes skin, subcutaneous tissue, striated and smooth tissue, muscle, cartilage,... mucous membrane, ...organs and glands. Surgical specialties and applications include general surgery, plastic surgery, aesthetic surgery, dermatology, urology, gynecology, genitourinary,..." For genitourinary surgery of soft tissue, one of the specific indications is "lesions of the external genitalia," which includes vulvar lichen sclerosus.

B3. DESCRIPTION OF RESEARCH PROTOCOL

A. Study Design – Overview, Methods, Procedures

Study Overview

This will be a non-randomized, open-label, prospective study. Participants will be recruited in general and subspecialty obstetric and gynecology clinics. Participants who meet all eligibility criteria, including providing written informed consent, will have three treatment visits and two follow-up visits in an outpatient setting. Participants will not be charged for any treatments.

At each treatment visit, participants will be asked to complete questionnaires to assess their symptoms. We also will take photographs of the affected area at the first and third treatment visits. Photographs will include only the area of lichen sclerosus, such that individuals cannot be identified in the photographs. Participant photographs will be taken using the BIDMC PhotoConsult iOS application that allows providers to upload photographs to a patient's online medical record through a secure application.

Women with biopsy-proven lichen sclerosus will be treated with the ProFractional hand piece using the sapphire plate stand-off (Sciton, Inc. Palo, Alto, CA). The laser energy is delivered in a scanning fractional pattern to ablate microchannels in tissue to allow faster healing. Treatment will be delivered in 3 sessions scheduled 4 weeks (+/- 1 week) apart.

Prior to receiving treatment, topical anesthetic will be applied to the affected area for 20-30 minutes and then wiped away. The treatment area will be cleaned and dried of any moisture prior to treatment. The disinfected standoff with sapphire plate will then be applied to the ProFractional hand piece. Based on the biopsy results, the appropriate ablation depth will be inputted with 11% treatment density selected. Each treatment will include two passes of the laser over the affected area.

- Visit 1, month 0: On the first pass, the depth of the laser will be from 300 to 500 microns, or the thickness of 3 to 5 sheets of paper; the depth will be based on the biopsy that was used to diagnosis the lichen sclerosus. On the second pass, the depth will be 50 microns deeper than the first pass and the hand piece rotated 45°.
- Visit 2, month 1: The first pass of the laser will be the same depth as the second pass from the last visit. The second pass will be 50 microns deeper and the hand piece rotated 45°.
- Visit 3, month 2: The first pass of the laser will be the same depth as the second pass from the last visit. The second pass will be 50 microns deeper and the hand piece rotated 45°.

Participants will return for follow-up visits at 1 and 3 months (months 3 and 5 of the study) following the third treatment.

- Visit 4. month 3
 - o Participants will be asked to complete questionnaires to assess outcomes.
- Visit 5. month 5
 - Participants will be asked to complete questionnaires to assess outcomes.
 - We will take photographs of the affected area.
 - Biopsy of area with lichen sclerosus; the biopsy will be done the same way as the one that was done to diagnosis your lichen sclerosus

If participants prefer not to come in person for Visit 4 due to concerns over COVID-19, they may have a telehealth visit instead to check in with their provider. In that case, the participant would complete the Visit 4 survey remotely, either over the phone with the study coordinator or online via REDCap.

Outcome Assessment

The primary outcomes will be change in histology and depth of disease from baseline to three months

after the last laser treatment. The baseline depth of lichen sclerosus will be based on the results of the clinical biopsy performed before study participation. We will use the study biopsy collected at the follow-up visit three months after the last treatment to determine resolution of disease or, if disease persists, to what depth. The biopsies will therefore serve as an objective means to determine effective treatment of disease.

The secondary outcomes will include the following:

- Change in symptoms and quality of life using the Vulvovaginal Symptom Questionnaire
- Change in symptom severity using the Patient Global Impression scales for severity and improvement
- Vulvar lichen sclerosus improvement as assessed using photographs. Photographs will be rated by observers blinded to whether a photo is before or after treatment.
- Satisfaction with treatment using a participant satisfaction questionnaire

B. Statistical Considerations

Sample size

Based on the limited prior data, we anticipate that 60% of participants will achieve the primary outcome, which is resolution of lichen sclerosus on biopsy at three months after completion of treatment. Using a one-sample binomial proportion test and assuming a two-sided alpha=0.05 and power=85%, we would need to 27 evaluable participants to show that 60% is statistically different from a reference proportion of 30%. To account for 10% potential loss to follow-up, we aim to enroll 30 participants.

Statistical Analysis

We will present data as mean (± standard deviation), median (interquartile range), or proportion, based on data type and distribution. Continuous data will be compared with the appropriate parametric or non-parametric test, accounting for paired data as needed. Categorical data will be compared with the chi-square, Fisher's exact, or McNemar's test. P values <0.05 will be considered statistically significant. Analyses will be conducted with SAS 9.4 (SAS Institute, Cary, North Carolina).

PI Revision Date: 10.29.2020

C. Participant Selection

Inclusion criteria

- Female
- Aged 18 years old or older
- · Biopsy-proven active vulvar lichen sclerosus
- Characteristic changes of vulvar lichen sclerosus on gynecological exam
- Self-reported indication of one or more of the following symptoms of lichen sclerosus
 - o Dryness
 - Itching
 - Burning
 - Bleeding
 - Blistering
 - Soreness
 - Easily bruises
 - Easily tears
 - Ulcerated lesions
 - Painful intercourse
- Ability to complete questionnaires in English
- Written, informed consent
- Willing and able to logistically follow schedule of treatments and follow-up visits

Exclusion criteria

- Receiving systemic immunosuppressant's (e.g. corticosteroids) within 4 weeks of enrollment
- Use of topical vulvar steroid-containing creams at the affected area within 4 weeks of enrollment
- Immunocompromised (e.g. lymphoma, AIDS, Wiskott-Aldrich syndrome)
- · History of uncontrolled malignant disease
- · Additional genital skin disease
- Known allergy or intolerance to topical anesthesia
- Known history of connective tissue disease
- Known propensity for keloid formations

B4. POSSIBLE BENEFITS

It is possible that participants may benefit from an improvement in their vulvar lichen sclerosus symptoms and quality of life. Patients with vulvar lichen sclerosus and their providers will benefit from the increased clarity on the effectiveness of laser treatments, potentially expanding the now limited treatment options available to those who are ineligible for high potent topical steroids or have failed topical treatment.

PI Revision Date: 10.29.2020

B5. POSSIBLE RISKS AND ANALYSIS OF RISK/BENEFIT RATIO

This study poses minimal risks to participants. As shown in a peer-reviewed study where the fractional Er:YAG laser was used to improve postsurgical facial scars from skin cancer surgery, adverse effects were limited to transient hyperpigmentation and erythema. ¹² The treatments will be carried out by skilled and trained providers. Any discomfort caused by the laser treatments themselves will be attempted to be mitigated by the application of topical anesthetic prior to treatments.

Other than potential discomfort from the laser, other risks include vulvar spotting (light bleeding), allergic reaction to topical anesthetic, and infection from the biopsy or the laser treatment

The only other foreseeable risk is that associated with participant confidentiality. To protect participant privacy, all data will be handled in a confidential manner. All electronic data will be kept in a password-protected folder on the BIDMC secure server behind the firewall or in REDCap. Any paper associated with the study will be kept in a locked office.

Risks associated with this study are minimal. Given the possible benefits both for participants themselves and scientific knowledge gained, the benefits are believed to outweigh the risks.

B6. RECRUITMENT AND CONSENT PROCEDURES

Recruitment

We will attempt to identify and recruit study participants at a clinical visit with gynecology, gynecologic oncology, radiation oncology, or surgical oncology. We will also post flyers at these clinics in order to inform potential participants about this study.

Consent

Written, informed consent will be obtained by members of the study team from participants prior to the collection of any data. Informed consent will occur in a private area; study staff will be able to answer any questions from potential participants. Potential study participants will be clearly informed that it is unclear whether fractional 29240 nm laser therapy is beneficial for symptoms of lichen sclerosus.

Participant Protection

All potential participants will be informed that participation in the study will in no way affect their clinical care. Written, informed consent will be obtained from all participants, and participants will be informed that they can withdraw from the study at any point.

B7. STUDY LOCATION

Privacy

All consent and data collection will be conducted in a private setting. The information being collected is limited to only the minimum amount of data necessary to accomplish our objectives.

Physical Setting

We have a dedicated procedure room where all laser treatments will be performed.

PI Revision Date: 10.29.2020

| D | D 4 : | T A C | | IDITY |
|-----|-------|-------|-----|-------|
| B8. | DA | IAS | ヒしい | IRITY |

| All electronic data will be kept in a restricted-access folder on the BIDMC secure server, behind the firewall or in REDCap. Any paper resulting from this study will be kept in a locked office belonging to a member of the study staff. | | | |
|--|--|--|--|
| B9 Multi-Site Studies | | | |
| Is the BIDMC the coordinating site? | | | |
| Is the BIDMC PI the lead investigator of the multi-site study? | | | |
| | | | |
| B10 Dissemination of Research Results | | | |
| We plan to present the data at national and international meetings and publish the results in a peer-reviewed journal. Data will be reported only in aggregate. | | | |
| | | | |

References

- 1. Arroyo C. Fractional CO(2) laser treatment for vulvovaginal atrophy symptoms and vaginal rejuvenation in perimenopausal women. Int J Womens Health. 2017 Aug 28;9:591-595. doi: 10.2147/IJWH.S136857. eCollection 2017.

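### Two sections of the protocol define the primary outcome differently, and nothing ranks change in disease depth against resolution on biopsy

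*Combined protocol and SAP*

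**What the plan says.** - **B3.A, Outcome Assessment**, uses the plural and speaks of change: "The primary outcomes will be change in histology and depth of disease from baseline to three months" after the last laser treatment. It adds that the biopsy at that visit will be used "to determine resolution of disease or, if disease persists, to what depth". Depth does not appear in the list of secondary outcomes that follows.
- **B3.B, Sample size**, uses the singular and a yes/no result: "the primary outcome, which is resolution of lichen sclerosus on biopsy at three months after completion of treatment". The reference rate (30%), anticipated rate (60%), two-sided alpha (0.05), power (85%) and 27 evaluable participants all belong to this outcome: "Using a one-sample binomial proportion test".
- **B3.B, Statistical Analysis**, names no primary analysis and does not repeat the binomial test. Depth falls under the general sentence: "Continuous data will be compared with the appropriate parametric or non-parametric test, accounting for paired data as needed". The threshold is the same for everything: "P values <0.05 will be considered statistically significant".
- **B1**, Aim 1, is also framed as change: "To assess physical and histological changes related to vulvar lichen sclerosus before and after laser treatment". B1 then states what the trial is for: "The results of this study will determine whether fractional 2940 nm laser is an effective treatment option for lichen sclerosus".

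**The concern.** The protocol gives two answers to the question of which result decides the trial. B3.A makes depth primary; B3.B leaves it out. Since depth is not a secondary outcome either, primary is the only status the document gives it. There is no testing order, no success rule and no named depth test.

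This matters because the two null hypotheses differ. Resolution is judged against 30%, which is the only comparator in a single-arm, open-label study. A paired depth test is judged against no change. Resolvers themselves pull average depth down, so depth can reach significance when the resolution rate merely equals the reference rate. Reporting that as a positive primary would answer an easier question than the one the trial was sized for, while B1 promises a determination of effectiveness. The concern is which question gets answered; inflation of the type I error rate is not claimed.

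**Working it through.** **1. Reproduce the sample size.** Inputs from B3.B: reference 0.30, anticipated 0.60, two-sided alpha 0.05 (0.025 in the upper tail), power 85%. Let X be the number of resolvers among n.

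| n | Smallest X with upper tail ≤ 0.025 | Power at 60% |
|---|---|---|
| 25 | 13 | 84.6% |
| 26 | 14 | 80.1% |
| 27 | 14 | 85.5% |

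So 27 is the smallest n with at least 85% exact power, and 27 / 0.90 = 30 enrolled. Both stated figures reproduce. The normal-approximation formula does not give 27: ((1.96 × √0.21 + 1.036 × √0.24) / 0.30)² = 21.96, so 22. The plan's N therefore fits an exact test of resolution. No calculation in the document covers depth.

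**2. The bar for resolution at n = 27.** P(X ≥ 14 | 0.30) = 0.0143, or 0.0285 doubled, so 14/27 (52%) is needed by the exact test. At 13/27 (48%) the upper tail is 0.0359: exact p = 0.072 doubled, or 0.056 by the minimum-likelihood method. The score form gives z = (0.4815 − 0.30) / √(0.21/27) = 2.06, p = 0.040. Because the analysis section does not name the version of the test, 13/27 could be called either way.

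**3. The bar for depth, simplest illustration.** Assume persisters show no change and resolvers are scored as depth zero. With k resolvers, all non-zero changes are reductions, and an exact paired test gives p = 2 × 0.5^k: 0.0625 at k = 5 and 0.031 at k = 6. Six of 27 is 22%, below the 30% reference.

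**4. How often depth could be significant with resolution not (X ≤ 13).** The documents give no depth SD, expected change or named test, so every depth input here is an assumption: baseline depth 400 microns (SD 60), resolvers going to zero, persister change as shown. Simulated trials of 27 with a true resolution rate of 30%:

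| Persister change: mean (SD), microns | Paired t | Signed-rank | Sign test |
|---|---|---|---|
| 0 (60) | 92% | 65% | 21% |
| 0 (120) | 81% | 65% | 20% |
| +50 (60) | 47% | 6% | 0% |
| +50 (120) | 41% | 22% | 2% |

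At the plan's anticipated 60%, the same four scenarios give about 13–15% (t), 9–15% (signed-rank) and 0–8% (sign test). The ceiling there is the chance that resolution fails, 1 − 0.855 = 14.5%, apart from simulation noise. The answer depends heavily on a test and on depth changes that the plan does not specify.

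**The case against.** The best defence is that the two sections largely agree. Every participant enters with biopsy-proven disease, so resolution on the later biopsy is itself a change in histology, and B3.B can be read as the working definition of that part of B3.A. The sentence on reading the biopsy puts resolution first and depth second. Only resolution has a test, a reference rate and power. Nothing says that depth alone is enough; the conjunction in B3.A could equally mean that both are required.

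This narrows the point chiefly to the status of depth but does not remove it. An order for reading a biopsy is not an order of testing, and a sizing basis does not withdraw the primary status that B3.A gives to depth. That the conjunction can be read as both-required, while B3.B requires resolution alone, shows that a rule is missing.

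The criticism of the simulated rates has more force. They score resolvers as depth zero, whereas the protocol speaks of depth where disease persists. If only persisters were tested and their mean change were zero, about 5% of two-sided tests would be significant, about 2.5% in the direction of benefit. The rates are also much lower at a true 60% than at 30%. And if 30% clear while the rest are unchanged, mean depth really has fallen, so a significant depth test would not be a false positive. The rates are illustrations, and the finding does not rest on them.

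**Conclusion.** The concern holds. B3.A and B3.B define the primary outcome differently, depth is ranked nowhere, and the text does not prevent a depth result alone from being presented as a positive primary. That follows from the wording and needs no assumption.

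The sample size is correct for resolution by the exact test (14 or more of 27, power 85.5%). The gap between the bars, 14 resolvers against as few as 6, assumes unchanged depth in persisters and resolvers scored as zero. Confidence is high in the inconsistency and low in how often the two outcomes would disagree. This should be corrected, but it does not undermine the design.

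**What to change.** Reconcile B3.A with B3.B and name the deciding outcome before outcome data are seen. Resolution is the natural choice because it alone is sized.

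- **B3.A, primary:** The single primary outcome is resolution of lichen sclerosus on the Visit 5 biopsy (yes/no).
- **B3.A, first secondary:** Change in depth of disease and other histologic change from baseline to Visit 5, reported as paired change with a 95% confidence interval. State how resolvers enter the depth analysis.
- **B3.B, Statistical Analysis:** The primary outcome will be tested with the exact one-sample binomial test against 30% at two-sided alpha 0.05. Depth and other histologic results are secondary and cannot by themselves make the trial positive.

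If the sponsor wants depth to remain primary, an explicit both-required or fixed-sequence rule would also resolve the mismatch, with the depth test named.

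With resolution as sole primary the cost is wording only: 27 evaluable, 30 enrolled and 85.5% exact power all stand. The sponsor gives up claiming a positive primary on depth alone, and naming the exact test means that 13/27 would not count as significant.

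### Does the biopsy timing, counted from the third, last or completing treatment, leave the 27 evaluable women without a single denominator?

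*Combined protocol and SAP*

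**What the plan says.** Section B3.A, Study Overview, plans three treatment visits and two follow-up visits for every participant, with sessions about four weeks apart (months 0, 1 and 2). On follow-up it says: "Participants will return for follow-up visits at 1 and 3 months (months 3 and 5 of the study) following the third treatment". The month-3 visit (Visit 4) has questionnaires only, and of that visit the protocol says: "If participants prefer not to come in person for Visit 4 due to concerns over COVID-19, they may have a telehealth visit instead". Visit 5 (month 5) has questionnaires, photographs and the only study biopsy.

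B3.A, Outcome Assessment, says: "We will use the study biopsy collected at the follow-up visit three months after the last treatment to determine resolution of disease". Depth, where disease persists, is read from the same specimen.

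B3.B, Sample size, describes the primary outcome as "resolution of lichen sclerosus on biopsy at three months after completion of treatment", and says "we anticipate that 60% of participants will achieve the primary outcome". It then says "we would need to 27 evaluable participants to show that 60% is statistically different from a reference proportion of 30"%, and "To account for 10% potential loss to follow-up, we aim to enroll 30 participants".

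Statistical Analysis names no analysis set. The only early exit described is in B6, Participant Protection: "participants will be informed that they can withdraw from the study at any point".

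**The concern.** The trial has no control arm, so the main result is one proportion tested against 30%. Whoever is in the denominator determines that proportion.

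The three timing phrases agree for a woman who has all three sessions. Suppose instead that she stops laser after session 1 or 2 and stays in the study. Three months from her last session is then month 3 or month 4. Month 3 is a questionnaire visit that may be remote, and month 4 has no visit. On one reading she could be evaluable with an unscheduled biopsy; on the other, three months from a third session never arrives for her. The 10% allowance is described as loss to follow-up and does not mention early stopping.

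If early stoppers resolve at a different rate from the others, counting them or leaving them out gives different answers. In an open-label study, that choice could be made with results in view.

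**Working it through.** **1. The plan's own figures.** Inputs from B3.B: reference 0.30, anticipated 0.60, two-sided alpha 0.05, power 85%, 10% loss.

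- Exact binomial test, upper tail at most 0.025. At n = 27 the smallest significant count is 14: P(X ≥ 14 | 27, 0.30) = 0.0143.
- Power: P(X ≥ 14 | 27, 0.60) = 0.855. Of the sizes from 20 upward, 27 is the first to reach 85% (n = 26 gives 80.1%, n = 25 gives 84.6%).
- Enrollment: 27/(1 − 0.10) = 30.

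Both figures reproduce. The 10% allowance removes 3 of 30 women and leaves 27 with an outcome. This already implies that evaluable means having the outcome biopsy.

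**2. The timing phrases side by side.**

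| Place | Anchor | Month if three sessions are given |
|---|---|---|
| B3.A, follow-up visits | third treatment + 3 months | 2 + 3 = 5 |
| B3.A, Outcome Assessment | last treatment + 3 months | 2 + 3 = 5 |
| B3.B, Sample size | completion of treatment + 3 months | 2 + 3 = 5 |

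Outcome Assessment refers to a specimen taken at a particular follow-up visit. Only Visit 5 includes a biopsy, so the sentence points to Visit 5 and does not set up a schedule that moves with each woman's last session. Biopsies at month 3 (0 + 3) or month 4 (1 + 3) appear nowhere in the text; they have to be inferred. The schedule also labels Visit 5 simply as month 5, and nothing bars a woman who missed a session from attending it and being biopsied.

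**3. How much the denominator could matter.** The documents give no early-stopping rate, so this step is assumption only. Let k of 30 women stop early and be biopsied with none resolved, let the other 30 − k resolve at 60%, and let nobody be lost. Use the exact test with p = 2 × upper tail.

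- k = 3, 14 resolved: 14/27 = 51.9% (95% CI 31.9% to 71.3%), p = 0.029; 14/30 = 46.7% (28.3% to 65.7%), p = 0.080.
- At n = 30 the smallest significant count is 15, so only a count of 14 reverses: P(X = 14 | 27, 0.60) = 10.5%.
- Probability of disagreement for k = 1 to 5: 0%, 8.4%, 10.5%, 12.7%, 26.1%. With the normal test: 0%, 0%, 7.0%, 9.1%, 19.0%.
- If the three early stoppers resolve at 30% instead of 0%, the 10.5% becomes 5.3%.

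**4. Power if early stoppers are simply left out.** Assume 30 enrolled, 3 lost, and m of the remaining 27 stopping early. The denominator is then 27 − m. For m = 1 to 5 it is 26, 25, 24, 23, 22, with exact power 80.1%, 84.6%, 78.7%, 83.6%, 77.2%. If those women are kept and also resolve at 60%, power stays at 85.5%.

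**The case for a change.** The strongest case for a change is that women may leave at any time, and a plan should say in advance how each treated woman is counted. The protocol's own background suggests that the denominator matters. In the earlier Er:YAG study it cites, 15 women enrolled and 7 were clear, reported as 58.3%. That is 7/12; over all enrolled it would be 7/15 = 46.7%. The fix would be cheap, and in the k = 3 example the gap is 85.5% against 75.0% power. If the true rate across all 30 women is 30%, leaving out three unresolved early stoppers gives an upper-tail false-positive rate of 3.6%, against 1.4% if they are counted.

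Part of this stands. Evaluable is undefined, and no rule covers a woman with fewer than three sessions or with no biopsy. The rest is weaker:

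- The two power figures compare different true rates (60%, and 0.60 × 27/30 = 54%), so the gap is not a loss caused by wording.
- The 3.6% sets the rate among the 27 at 9/27 = 1/3. It is an error rate only if all 30 women are the target, which is the question at issue.
- The earlier study's 3 missing women are unexplained, so they give no early-stopping rate. Its 58.3% fits a biopsied-only denominator, the same basis that the sizing implies here.
- Choosing between readings after the fact would need month-3 or month-4 biopsies, which the schedule does not collect.
- Aligning the three phrases would still not say who is evaluable. A supporting rate in all treated women, with missing biopsies counted as unresolved, addresses missing data rather than timing.

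**Conclusion.** The claimed contradiction does not hold. Under the planned three sessions, *third*, *last* and *completion* name one event and lead to one biopsy at month 5. The figures 27 and 30 are correct.

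What is left is a gap that analysts fill sensibly. Followed as written, the plan biopsies women at Visit 5, tests the proportion resolved among those biopsied against 30%, and gives a sound result. Good reporting would state the numbers treated and biopsied, the sessions received and the reasons for missing biopsies. That replaces no stated method and does not alter the test or the enrollment.

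The effect is nil for women who complete treatment. With one unresolved early stopper the disagreement probability is 0% under both tests. Larger values (10.5% at k = 3, 26.1% at k = 5, exact test) require several women to stop laser, stay in the study, be biopsied and all remain unresolved, with nobody lost. The documents support none of these assumptions, and entry requires that women can keep to the schedule (B3.C). Frequent early stopping with continued follow-up would make the missing definition matter more, but nothing in the protocol suggests it.
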